### 2.2.7 Study Measures and Data Collection Schedule

Assessments will occur at baseline, 6, 12, and 18 months on clinical, behavioral, and psychosocial outcome measures and potential effect modifiers and mediators at one of the PAMF clinics from which participants are recruited (**Table 4**). Trained bilingual and bicultural research assistants blinded to participants’ random assignment will conduct assessments using standardized measurement protocols and equipment and previously validated interviewer-questionnaires (in-person or by phone). For in-person data collection, participant’s preferred time and location will be accommodated whenever possible, including evenings and weekends. We will also utilize self-administered questionnaires online, which we have shown to be acceptable and feasible in previous trials with Latinos. We will use Spanish or English as indicated by the participant.

#### 2.2.7.1 Primary and Secondary Outcomes

The primary outcome is proportion of participants who sustain at least 5% of baseline weight loss at 18 months. Research assistants will weigh participants in duplicate using a standard

calibrated scale at baseline and 18 months at local clinic sites as in previous and ongoing trials. The primary outcome was selected based on its clinical relevance for patients, providers, and health care systems, as well as patient and stakeholder input. Weight loss of  $\geq 5\%$  of baseline weight is known to confer a reduction in risk of diabetes and other chronic disease. This outcome emphasizes chronic disease prevention by focusing on clinically relevant weight loss. Our patient advisors advocated for this primary outcome because their primary goal for the intervention is to reduce the risk for chronic disease. We will examine three types of secondary outcomes:

**Health behaviors** (dietary intake, physical activity, and sedentary behavior) and psychosocial well being will be collected via phone or online questionnaire at baseline, 6, 12, and 18 months (Aim 2). Dietary intake will be assessed using the gold-standard approach of multiple pass 24-hour recalls in Spanish or English by highly trained and experienced staff, over the phone, at baseline and 18 months. Physical activity and sedentary behavior will be assessed using the interviewer-administered 7-day Physical Activity Recall and a self-report measure of sedentary behavior over the phone at all time points. Participants will complete online questionnaires that we have successfully used in prior trials to assess psychosocial well-being (e.g., EuroQol EQ-5D, PHQ-9 for depression). If needed, a research assistant can help a participant fill out the online questionnaire at an office visit.

**Cardiometabolic risk factors** (blood pressure and waist circumference) measured at baseline and 18 months (Aim 2). Trained research assistants will conduct blood pressure and waist circumference measurement according to standard protocols. Waist circumference will be measured in duplicate at the right iliac crest, in centimeters as per previously published protocols.

**Body Weight from the EHR up to 24 months post-randomization.** We will abstract weight measurements from the EHR 3 months prior to randomization and up to 24 months post-randomization to examine trajectories of weight loss over time. We examined the feasibility of this approach by comparing data on researcher-measured weights and EHR-weights in two prior behavioral lifestyle intervention trials. Using data from two prior trials we observed that participants had a sufficient number of weight measurements in the EHR and there was excellent agreement between researcher-measured weights and weight obtained in the EHR.

#### 2.2.7.2 Potential effect modifiers and mediators

We will collect information on potential effect modifiers at baseline including demographic characteristics (e.g., race/ethnicity, marital status, education), technology utilization, and health literacy. For technology utilization, we adapted a survey from the Pew Hispanic Trust on technology access and usage. For health literacy, we will use the newest vital sign, which uses a food nutrition label. Additionally, at each time period, we will collect information on theoretically-based core constructs shown to predict weight loss and behavior change in diverse populations including outcome expectancy, self-efficacy, and social support. These putative mediators are directly informed by Social Cognitive Theory, the theoretical base of HOMBRE and the GLB.

**Table 4. Outcomes, potential effect modifiers and mediators measured at baseline visit (BV), 6, 12, and 18 months (M)**

Outcomes	Measures	Mode	BV	6M	12M	18M
Primary outcome:	Height	In-person	X			
Proportion losing ≥ 5% of baseline weight at 18 months	Weight - standardized methods 	In-person	X			X
Secondary outcomes:	Weight	EHR	Ongoing -> 24 months			
Clinical: Weight change and cardiometabolic risk factors	Waist circumference	In-person	X			X
	Blood pressure- standardized methods 	In-person	X			X
Behavior change:	1. Multiple pass 24-hour diet recall 	Phone	X			X
1. Dietary intake	2. 7-day Physical Activity Recall, 		X	X	X	X
2. Physical activity	3. Sedentary behavior questionnaire 		X	X	X	X
3. Sedentary behavior						
Psychosocial well-being:	1. EuroQol EQ-5D 	Online	X			X
1. Health-related quality of life	2. Obesity-related Problem Scale 					
2. Obesity-specific quality of life	3. Perceived Stress Scale & Nine-item Patient Health Questionnaire (PHQ-9) 					
3. Depressive symptoms	4. PROMIS™ sleep disturbance and Sleep-Related Impairment 					
4. Sleep habits and quality						
Potential modifiers:	1. Age, race/ethnicity, education, employment, occupation, marital status, household size, income, acculturation	In-person	X			
1. Demographics						
2. Technology utilization	2. Adapted from the Pew Hispanic Trust technology use and access survey 	Online	X			
3. Health literacy	3. The newest vital sign 	In-person	X			
Potential mediators:	1. Goals and Relative Weights,  Stunkard silhouettes 	Online	X	X	X	X
1. Outcome expectancy	2. Weight Efficacy Life-Style Questionnaire,  Self-Efficacy for Dietary Change and Exercise 					
2. Self-efficacy	3. Social Support for Diet Change & Exercise 					
3. Social support						
Intervention engagement:	1. Attendance at sessions (in-clinic or online) and tracking of online video viewing	Mobile app	Ongoing			
1. Session attendance	2. Tracking of messages sent/received to coach					
2. Interaction with coach	3. Self-tracking of physical activity, diet, and weight on app or web					
3. Self-tracking						

### 2.2.7.3 Evaluation for implementation and dissemination

To complement the focus on effectiveness in Aims 1 and 2, we will assess the potential for implementation and dissemination using the RE-AIM framework's reach, adoption, implementation, and maintenance domains (**Table 5**), as we have done in other studies via interviews with study staff, coach, participant, and primary care and community stakeholders. We will conduct a detailed evaluation of these RE-AIM domains with mixed methods to gain a nuanced understanding of why the intervention is (or is not) superior to the minimally intensity intervention control, whether high intervention fidelity is achieved, what barriers and enablers there are, how these may translate into future implementation and dissemination, and what modifications can maximize implementation success. All interviews will be recorded and transcribed. Transcriptions of interviews with Latino patients will be translated to English.

Table 5. Summary of quantitative and qualitative measures for the process evaluation		
	Example Questions, Data Sources, and Methods	
RE-AIM Domains	Quantitative	Qualitative
Reach of the intended target population	Patient survey & recruitment tracking data: percentage and characteristics (e.g., language preference, place of birth, years in the US) of participants compared with non-participants.	Interviews with study staff: Barriers enablers of recruitment, recruitment variability by demographics or other characteristics, strategies for addressing barriers, potential strategies to maximize reach.
Adoption by target staff or settings	Administrative data: Characteristics of participating clinics, percentage and characteristics of PCPs approached who participated (e.g., PCPs referring or approving patients for study screening).	Interviews with PCPs and clinic leadership: Barriers and enablers of clinic and provider participation, recommendations for reducing barriers and maximizing adoption.
Implementation success during intervention delivery ( staff perspective )	Surveys of lifestyle coach: perceptions of (1) consistency of intervention procedures with available evidence, (2) intervention suitability for primary care, and (3) experience with the strategies facilitating intervention delivery based on the Promoting Action on Research Implementation in Health Services model. 	Interviews with lifestyle coach, PCPs, and clinic leadership: Barriers and enablers of delivering the intervention and differences across participating clinics, modifications to maximize implementation success?
Implementation success during intervention delivery ( patient perspective )	We will assess intervention participants' engagement and adherence by monitoring the number of group sessions attended, reasons for missed sessions, secure messaging and self-monitoring frequency, and adherence across participant subgroups.	Interviews with a random sample of participants: Relevance and acceptability of knowledge and skills, frequency of practicing intervention strategies, perceived benefits, problems encountered, cultural congruence, satisfaction with program format, materials, and coach performance?
Maintenance of intervention effects in individuals and settings over time	We will assess attrition and adverse events by participant characteristics and treatment condition.	Interviews with lifestyle coach, PCPs, and clinic leadership: Potential for integration into regular care and sustained, resources, policies, and care process redesigns needed to maximize sustainability.

### 2.2.8 Retention

As we have done in our previous trials, we will maximize adherence and retention by careful selection and training of staff, systematic quality control, and adhering to high-quality practices to maintain participation in the study. We will use a tracking database to facilitate coordination and monitoring of participant-level activities. No individuals will be randomized without eligibility verification or complete baseline data. Examples of processes that facilitate retention at follow-up include thorough and fully informed roles and responsibilities of staff and participants, conveying an appreciation of participation and study identification, nominal remuneration for study visits, reasonable accommodations to participant schedules, and prudent participant incentives (pedometer and cash incentives). We will contact participants who miss a visit to reschedule and re-engage them in subsequent follow-ups. Using a combination of these strategies, we have consistently achieved high retention in several RCTs of similar scope (82%-92%), including those with Latino participants (85%).

### 2.2.9 Statistical Analysis

#### 2.2.9.1 Analytical Plan

Aim 1 and 2: The primary hypothesis that HOMBRE will lead to a greater percentage of Latino men who sustain  $\geq 5\%$  of baseline weight loss through 18 months than the minimal intensity intervention control group will be tested with a generalized linear mixed model.

$$Y = \beta_0 + \beta_1 X + \beta_2 Y_0 + \sum \beta_{4+i} Z_i + \alpha + \gamma + e \quad (1)$$

Let  $Y$  be the outcome of interest for a patient randomized to arm  $X$  (HOMBRE or control). Given the covariate-adaptive randomization, distributions of baseline values on the outcome variable ( $Y_0$ ) and key characteristics ( $Z_i$ ) should be similar between study arms and thus not bias the results. But to the extent they are associated with the outcome, their inclusion in the analysis will account for otherwise unexplained variation and hence increase efficiency.  $\alpha$  and  $\gamma$  are clinic and PCP nested within clinic random effects, and  $e$  is the random error term. Aim 2 examining secondary outcomes at 18 can be evaluated by adapting the same model. The outcome variables in Aim 2 (e.g., cardiometabolic, health behavior, and psychosocial well-being indicators) will be continuous. We will model the change from baseline in each indicator as the outcome  $Y$  and the fixed and random effects will remain the same as described in model (1).

Primary analyses will follow intent to treat principles. We will verify that mixed model-based results are not sensitive to violations of model assumptions with permutation and bootstrap resampling tests. We will document the extent, pattern, and reasons for missing data, and will conduct sensitivity analyses of the impact of missing data on stability of the primary results. For example, we may use weight data up to the point when they are no longer available (e.g., dropouts) or should not be used, and then employ multiple imputation based on a predictive distribution for future weights.

Exploratory Aim 1: Weight loss trajectories using weight data from the EHR will be examined using tests of group-by-time interactions in mixed-effects growth curve model.

$$Y_t = \beta_0 + \beta_1 X + \beta_2 Y_0 + (\beta_3 + \beta_4 X) T + \sum \beta_{4+i} Z_i + \alpha + \gamma + b_0 + b_1 T + \varepsilon \quad (2)$$

Let  $Y_t$  be the outcome of interest at follow-up time  $T$  on a patient randomized to arm  $X$  (HOMBRE or control). Baseline values on the outcome variable ( $Y_0$ ) and key characteristics ( $Z_i$ ) will be included for efficiency as in model 1.  $\alpha$  and  $\gamma$  are clinic and PCP nested within clinic random effects as in model 1,  $b_0$  and  $b_1$  account for random intercepts and random slopes, and  $\varepsilon$  is the random error term. We will use a goodness-of-fit test to determine whether to include the quadratic or higher order of growth curves.

Exploratory Aim 2: We will also conduct exploratory subgroup analyses to evaluate potential effect modifiers for the primary outcomes by expanding equation 1 to include appropriate modifier-by-group interaction terms. In this context, testing whether the  $\beta$  coefficients of the interaction terms are equal to zero is equivalent to testing the null hypothesis that the variable of interest does not independently modify the intervention effect. Mediation (e.g., change in self-efficacy and its mediating effect on weight loss outcome) will be examined by MacKinnon's product of coefficients test ( $\alpha\beta$ ). Asymmetric confidence limits will be constructed based on the distribution of the product with the PRODCLIN program. Because multicollinearity may be present in multiple mediator models, we first will test each mediator in single-mediator models. Multiple-mediator models including all variables that are at least marginally significant in the single-mediator models will test for independent and suppression effects. To determine the extent of mediated effect, the percentage of total effect mediated will be calculated for each significant mediator as  $\alpha\beta/(\alpha\beta + \gamma)$ , where  $\gamma$  is the direct intervention effect on outcome. The effect modification-mediation analyses are hypothesis-generating, but we pre-specify the variables to ensure a focus.

**Aim 3:** For quantitative data collected as part of the assessment testing the potential for future implementation and dissemination, we will use t-tests for continuous variables and chi-square tests for categorical variables. For qualitative data collected related to aim 3, we will use NVivo, a multifunctional software system, to help code and manage data from the interview transcripts. We will initially use the interview guide to organize and provide a starting list of codes related to the factors associated with participant's values and preferences related to weight, diet and physical activity which we will supplement with emergent codes to capture new factors that arise from the group discussion. Two project team members will independently code the transcripts. Discrepancies in initial coding will be solved by discussion between project team members. Based on these discussions, the raters will conduct a final code of the transcripts. The general categories of codes will relate to modality, presentation, messages or motivations for weight loss important to men. Intercooder agreement will be quantified and reported for each coding domain using Cohen's Kappa, which is calculated as follows:  $(\text{Observed agreement} - \text{Chance}) / (1 - \text{Chance})$ . If substantial intercooder disagreements exist, a third project team member will review the text in question to determine appropriate coding before finalizing the coding scheme.

The purpose of the exploratory aim 2 & 3 analyses are to identify hypotheses for future rigorous studies. This study was not designed to have sufficient power to test the outcomes in exploratory analyses. In this case, multiple comparisons corrections will not be necessary.

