### 2.2.3. Randomization and Blinding

Latino men deemed fully eligible will be randomized in a 1:1 ratio to receive the HOMBRE intervention or a minimal intensity intervention (control  $n=212$ /arm). Men will be informed of their treatment assignment and invited to an orientation visit. We will apply a covariate-adaptive biased coin method that we have published and used successfully in several trials to achieve good marginal balance between treatments across the following baseline characteristics: clinic, age, BMI, level of acculturation assessed by the Short Acculturation Scale for Hispanics, and number of cardiometabolic risk factors. The dynamic block randomization algorithm of our method automatically ensures allocation concealment. By design, treatment will be identifiable to participants and the lifestyle coach, but masking of the investigators, safety officer, outcome assessors, and data analyst will be enforced. Regardless of random assignment, all participants will continue to receive usual medical care.

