### 2.2.4. Orientation Visit

Following randomization, all participants will be scheduled for an orientation group session specific to their randomization arm. The orientation session will be led by a bilingual and bicultural lifestyle coach and a research assistant focused on the technology components (fitness tracker and Smartphone application). Participants in both arms will be encouraged to bring their partner and/or other family members to the orientation session with the purpose of increasing understanding and social support among family members as advocated by the Latino Patient Advisory Board in the cultural adaptation process. Group orientation sessions for both arms will feature a didactic component to provide information on the background and goals of the intervention and an interactive small group discussion component.

The small group component for the HOMBRE intervention will engage participants in a discussion on the advantages and disadvantages of the three delivery options: self-directed via online videos, coach-facilitated via in-person groups, and coach-facilitated via online videoconferencing groups. Following the small group discussion, men randomized to the HOMBRE arm will select their preferred option using a structured handout that guides them through important decision domains including preferred level of coach and peer support, comfort

with technology, and lifestyle factors (e.g., work and family schedule). Men will be encouraged to discuss their choice with their partner and family if appropriate. The small group discussion component for the minimal intensity intervention will focus on identifying challenges and potential solutions to intervention adherence. At the conclusion of the orientation session, men in both arms will receive their intervention materials and any needed technology support.

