### 2.2.5.3 Minimal Intensity Intervention

Men randomized to the minimal intensity intervention group (control) will be offered a self-directed lifestyle program over a 12-month period. The program is based on the Group Lifestyle Balance (GLB) intervention, a group-based adaptation of the original DPP intervention. The GLB program's feasibility and effectiveness in primary care, and other community settings, are well documented. The GLB is an approved curricula for application of the CDC Diabetes Prevention Recognition Program, including electronically delivered modalities. The goal of GLB is to promote 5-10% weight loss as recommended by obesity treatment guidelines and a minimum of 150 minutes per week of moderate-intensity physical activity (e.g., brisk walking) as recommended by the 2008 Physical Activity Guidelines for Americans. The GLB supports participants in making healthy lifestyle changes to improve weight and prevent diabetes using theoretically-based behavioral strategies such as self-monitoring, goal setting, action planning and problem solving. Participants receive access to 12 program videos, available online, and written information to use in completing home-based, independent activities designed to help them problem-solve challenges they may face in losing weight and increasing physical activity (**Table 2**). The videos are available in English, with Spanish subtitles. A trained PAMF health coach is available upon request to answer participants' questions by telephone, email, mobile text messaging or secure messaging through PAMF's secure patient portal known as My Health Online.

	Options in HOMBRE			Minimal intensity intervention control
	Self-directed*	In-Person*	Videoconferencing*	
12 weekly core Sessions	Home, DVD or online (30 minutes/session)	Clinic, in-person, coach-led groups (45-60 minutes/session)	Remote, coach-led groups via video conferencing (45-60 minutes/session)	Home, DVD or online
Level of coach support	Medium: Standardized messages	High: Coach-led group, individualized feedback, standardized messages	High: Coach-led group, individualized feedback, standardized messages	Low: Coach available to answer participant questions
Type of peer support	None	Group: In-person groups	Group: Online groups	None

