Use of technology	High: Videos online or DVD; messages via self-monitoring app	Medium: Messages via self-monitoring app	High: Video conferencing, messages via self-monitoring app	Medium: Videos online or DVD, optional messages via self-monitoring app
Convenience	High: Engage in intervention at self-determined time and place	Low: Come into clinic at a time determined by group (several times offered)	Medium: Join groups from any location at time determined by group (several times offered)	High: Engage in intervention at self-determined time and place
*self-directed: self-directed via online/DVD videos in-person: coach-facilitated via in-person groups videoconferencing: coach-facilitated via online groups				

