#### 2.2.5.4 HOMBRE Intervention

Men randomized to the HOMBRE intervention group will be offered three intervention delivery options from which they can choose one. All three options are based on the GLB program over a 12-month period. Similar to GLB, the HOMBRE intervention includes 12 weekly sessions during the intensive phase (Months 1-3) and 10 biweekly or monthly contacts during the maintenance phase (Months 4-12).

The three delivery options are: 1) self-directed via online videos or DVD (referred to as self-directed), 2) coach-facilitated via in-person groups (referred to as in-person), and 3) coach-facilitated via online groups (referred to as videoconferencing). The primary difference across delivery options is how men engage in the weekly sessions during the intensive phase (**Table 2**). In the self-directed option men will view 12 videos (15-30 minutes each) online or via DVD during the intensive phase. The in-person group option includes 12 coach-facilitated group sessions at the clinic for the intense intervention phase. The coach-facilitated via online group option is similar to the in-person option but the meetings will take place via cloud-based video conferencing called Bluejeans. Participants can join over the internet or with a free smartphone application. The only hardware required is a computer or smartphone with an internet connection and speaker/microphone functionality. Participants will attend the sessions at specified times, but can join from wherever is convenient. All three options deliver the GLB, and encourage web/mobile-based self-monitoring using Myfitnesspal and the wearable activity tracker. Men will choose their delivery option in the group orientation visit as described above. The lifestyle coach will reach out to men who have achieved less than 2% loss of their baseline weight by four weeks to see if a different delivery option is better. Changing options is possible because all three approaches offer the same content.

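### Model (1) and the Aim 2 models ignore HOMBRE delivery groups; positive within-group correlation would make the 18-month intervals slightly too narrow, and a group-robust companion analysis would fix this cheaply

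*Combined protocol and SAP*

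**What the plan says.** Section 2.2.9.1 gives one mixed model for the primary outcome. Its two random terms "are clinic and PCP nested within clinic random effects, and" the only other random component is the error term. For Aim 2 the section states that "the fixed and random effects will remain the same as described in model (1". It also plans to verify that results are "not sensitive to violations of model assumptions with permutation and bootstrap resampling tests", without naming the unit to be resampled.

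Delivery differs between the arms. Section 2.2.5.4 states: "The in-person group option includes 12 coach-facilitated group sessions at the clinic for the intense intervention phase". The videoconferencing option has the same structure online. Table 2 gives the peer support of the in-person option as "Group: In-person groups" and gives none for self-directed HOMBRE men or for controls. On convenience it says of the in-person option "Come into clinic at a time determined by group (several times offered". The one group contact common to both arms is orientation: "all participants will be scheduled for an orientation group session specific to their randomization arm".

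Section 2.2.10 claims 80% power with 212 men per arm for a 15-point difference, allowing for 80% retention. It mentions no group size, ICC or design effect.

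**The concern.** Men who share a coach-led group for 12 sessions may end up with similar outcomes. The protocol's own theory points that way: Section 2.2.5.1 says social support strengthens self-efficacy, and Table 4 lists social support as a mediator. Lasting correlation of this kind would arise mainly in one arm, which makes the design partially nested.

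The existing random effects do not stand in for it. Clinic is a balancing factor and contributes men to both arms, so clinic effects largely cancel in the arm difference. Delivery groups lie wholly inside HOMBRE, so their variance adds to the variance of the difference. Videoconference groups can be joined from anywhere and need not follow clinic. A bootstrap that resamples individual men would miss the same dependence.

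At stake are the width of the primary and Aim 2 intervals and, to a lesser degree, the stated power.

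**Working it through.** **Inputs from the documents.** 212 per arm, 15 points, two-sided alpha 0.05, 80% retention (Section 2.2.10), so n = 212 × 0.80 = 169.6 evaluable men per arm. The control rate is described only as slightly below 39%; 35% is assumed here, giving 35% versus 50%.

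**Reproducing the stated power.** With pooled variance under the null and independent men:
- SE0 = √(2 × 0.425 × 0.575 / 169.6) = 0.0537
- SE1 = √((0.35 × 0.65 + 0.50 × 0.50) / 169.6) = 0.0531
- Power = Φ((0.15 − 1.96 × 0.0537) / 0.0531) = 80.1%

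The 80% figure is reached with no allowance for clustering.

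**Assumptions.** ICC, group size and uptake are not in the documents.
- Group size: four cohorts give 212 / 4 = 53 HOMBRE men each. Two thirds of 53, split evenly over two formats and two languages, is 8.8 enrolled or 7.1 evaluable per group. With two meeting times it is 4.4 enrolled or 3.5 evaluable. Ten is taken as an upper case.
- Uptake of a group option: q = 2/3.
- ICC at 18 months: 0.01 to 0.05.

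**Formulas**, with m evaluable men per group:
- Design effect in the HOMBRE arm: DE = 1 + q(m − 1) × ICC; control arm 1
- SE1² = (p0(1 − p0) + DE × p1(1 − p1)) / n
- SE0² = p̄(1 − p̄)(1 + DE) / n
- Coverage of the interval that ignores groups = 2Φ(1.96 × SE_naive / SE1) − 1, where SE_naive is SE1 with DE = 1
- Power of a correctly sized test = Φ((0.15 − 1.96 × SE0) / SE1)

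Example, ICC 0.05 and m = 10: DE = 1 + (2/3) × 9 × 0.05 = 1.30. SE1 = √((0.2275 + 1.30 × 0.25) / 169.6) = 0.0571 against a naive 0.0531, so coverage is 93.2%.

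| ICC | Coverage (%), m = 3.5 / 5 / 7 / 10 | Power (%), m = 3.5 / 5 / 7 / 10 |
|---|---|---|
| 0.01 | 94.9 / 94.8 / 94.8 / 94.6 | 79.7 / 79.5 / 79.3 / 78.9 |
| 0.02 | 94.8 / 94.7 / 94.5 / 94.3 | 79.4 / 79.0 / 78.5 / 77.7 |
| 0.05 | 94.5 / 94.2 / 93.8 / 93.2 | 78.4 / 77.4 / 76.1 / 74.3 |

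**Aim 2** (continuous, equal SD in both arms assumed). The ratio of true to modelled SE is √((1 + DE) / 2): 1.008 to 1.030 at ICC 0.02 and 1.021 to 1.072 at ICC 0.05.

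**Where power holds.** With 85% retention (the figure Section 2.2.8 gives for trials with Latino participants; n = 180.2), power at ICC 0.02 is 81.8 to 80.1%, and at ICC 0.05 it is 80.8 to 76.8%. With 80% retention, groups of 10 and a control rate of 26% or 18%, it is 81.4% or 87.0% at ICC 0.02, and 78.0% or 84.1% at ICC 0.05.

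**Choice of correction.** Simulations used 170 men per arm, a binary outcome, and two thirds of HOMBRE men in 28 / 23 / 16 / 11 groups of 4 / 5 / 7 / 10. The ANOVA estimate of between-group variance was zero or negative in about 40-42% of trials at ICC 0.02 and 23-30% at ICC 0.05. A random-effect model would then tend to return the uncorrected interval. A group-robust interval (factor K/(K − 1), K groups) covered 94.1-95.1% in every setting.

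**The case against.** The strongest reply is that the effect is too small to matter. Group sessions end at month 3, later contact is by individual phone call, and the outcome comes 15 months after the last session. The documents speak of a single coach ("treatment will be identifiable to participants and the lifestyle coach") and standardized materials, so there is little between-coach variation. In-person groups meet at a clinic, so the clinic effect may absorb part of their correlation. Covariate adjustment, which the plan adopts for efficiency, could offset a one- or two-point loss of power. The assumed control rate matters more: with no clustering, power is 80.1%, 83.6% and 89.0% at 35%, 26% and 18%. The bootstrap and permutation checks are already aimed at failed model assumptions, and independence is one of these.

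Most of this stands, and it limits the size of the point. It does not remove it. Clinic cannot represent videoconference groups. A bootstrap with no stated unit cannot be relied on to detect group dependence. Any positive ICC acts in the same direction on the intervals.

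A reader might infer more: that the primary test has a seriously inflated type I error, or that the trial is underpowered. The documents do not support either. Under the sharp null that treatment changes nobody's outcome there is no inflation; it needs group effects that average to no arm difference. Even then the formula gives 5.2-5.7% at ICC 0.02 and 5.5-6.8% at ICC 0.05. Much larger figures, such as 13-16%, need an ICC of 0.10 with groups of 20. The documents give no such values, and about 35 grouped men per cohort (two thirds of 53), spread over two formats and two languages, would hardly form groups of that size.

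**Conclusion.** The omission is plain from the text: delivery groups exist only in the HOMBRE arm, and neither the models nor the sample size allows for them. The consequence is conditional and probably small. On the assumptions above, the 95% intervals cover about 94.9% to 93.2%, and a correctly sized test has about 80% to 74% power, with the lower ends requiring ICC 0.05 and groups of 10. These are unadjusted two-proportion approximations to model (1). Power stays above 80% at ICC 0.02 if retention is 85% or the control rate is 26% or lower; under-coverage remains whenever the ICC is positive. This is a cheap improvement to consider, not a flaw that threatens the primary conclusion.

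**What to change.** 1. Record delivery-group ID with session attendance, which Tables 4 and 5 already track.
2. Keep model (1). For the primary and Aim 2 outcomes, prespecify a companion analysis with the same fixed effects plus clinic, and with standard errors clustered on first-assigned delivery group using a small-sample correction. Control, self-directed and never-assigned men are singletons. Men who change option stay in their first-assigned group.
3. In the planned bootstrap, resample whole HOMBRE groups.
4. Do not rely on a delivery-group random effect as the main correction. Its variance estimate would often be zero, and the interval would then be left uncorrected.
5. Add to Section 2.2.10 that the 80% power figure assumes no within-group correlation. A table by ICC and group size is optional.

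The cost is SAP wording, one extra recorded field and slightly wider intervals in the companion analysis. Enrolment is unchanged. The method should be fixed before unmasking, and group membership is harder to reconstruct if it is not recorded.
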